Table 13-2 Urinalysis clinically notable values

Parameter	Abnormality
WBC	>5
RBC	>5
Protein	+ or greater*
Glucose	+ or greater*
* Trace should proceed +, otherwise ++ or greater	

Table 13-3 Vital sign clinically notable values

Vital Sign	Age group	Notable criteria
Heart Rate	<12 years	>130 bpm or increase of ≥ 15 bpm from baseline Or <70 bpm or decrease of ≥ 15 bpm from baseline
	≥ 12 years	>120 bpm or increase of ≥ 15 bpm from baseline Or <50 bpm or decrease of ≥ 15 bpm from baseline
Systolic Blood Pressure	<12 years	≥ 125 mmHg or increase of ≥ 20 mmHg from baseline Or ≤ 70 mmHg or decrease of ≥ 20 mmHg from baseline
	≥ 12 to <18 years	≥ 160 mmHg or increase of ≥ 20 mmHg from baseline Or ≤ 90 mmHg or decrease of ≥ 20 mmHg from baseline
	≥ 12 years	≥ 180 mmHg or increase of ≥ 20 mmHg from baseline
Diastolic Blood Pressure	<12 years	≥ 85 mmHg or increase of ≥ 15 mmHg from baseline Or ≤ 50 mmHg or decrease of ≥ 15 mmHg from baseline
	≥ 12 to <18 years	≥ 95 mmHg or increase of ≥ 15 mmHg from baseline Or ≤ 50 mmHg or decrease of ≥ 15 mmHg from baseline
	≥ 12 years	≥ 105 mmHg or increase of ≥ 15 mmHg from baseline
Temperature	≥ 18 years	≥ 38.3 °C or a change of 1.1 °C

Vital Sign	Age group	Notable criteria
		from baseline
Weight		≥7% decrease from baseline weight

14 Appendix 2: Guidelines for first dose monitoring

Patients must have their first intake/injection of study drug in the Core and Extension Phase at the site and monitored by the independent First-dose Administrator. An ECG must be obtained and evaluated prior to the first dose of study drug and 6 hours after. Baseline or pre-dose ECG should be available for comparison to the post-dose ECG. Sitting heart rate and blood pressure must be measured prior to the first dose of the study drug and then every hour for at least 6 hours thereafter.

When obtaining the sitting heart rate the patient should be allowed to rest for 5 minutes. Prior to the first dose of study drug, the sitting heart rate and blood pressure measurements should be repeated twice to produce three readings for both heart rate and blood pressure.

Patients should receive the first dose of study drug before 12:00 PM (noon) at the site.

Patients may be discharged after 6 hours ONLY if the following discharge criteria are met:

- Heart rate (sitting) at discharge must be at least 55 bpm (in patients 12 years or older) or 60 bpm (in children below 12)
- Heart rate (sitting) at discharge must not be the lowest hourly value measured during the observation period (which would be suggestive of a continuing progressive decline in heart rate)
- Patients must have no symptoms in sitting or standing position associated with decreased heart rate or received treatment for bradycardia
- ECG at 6 hours should not show any new significant abnormalities, other than asymptomatic sinus bradycardia, not observed at the patient's pre-dose ECG (e.g. prolongation of QT/QTcF interval, persistent new onset 2nd degree (Mobitz Type I (Wenkebach) or higher AV block, 3rd degree AV block at any time during monitoring).

The same monitoring procedure applies also to the re-initiation of study drug after interruption ([Section 5.5.5](#)) and at the time of individual dose-increase ([Section 3.3](#)). In the Core Phase, re-initiation of study drug monitoring must be done by the independent first dose monitoring team in order to maintain the blind. However, in the Extension Phase monitoring for re-initiation of study drug or dose increases may be conducted by the main study team.

Patients who are off study drug treatment for the following durations:

- The treatment lasted for 14 days or less and was interrupted for 1 day or more, or
- The treatment lasted for more than 14 days and less than 29 days and was interrupted for more than 7 consecutive days, or
- The treatment lasted for 4 weeks or more and was interrupted for more than 14 consecutive days.

Patients should have written instruction on when to return to the clinic and a 24 hour contact phone number to call in the event of any new or warranted symptoms (chest pain, dizziness, palpitations, syncope, nausea, vomiting, etc.).

If the above discharge criteria are not met, patients should continue to be observed until they are met (the observation must last for at least 2 hours even if the criteria are met earlier).

However, patients experiencing any symptomatic event associated with reduction of the heart rate, a heart rate of < 45 bpm at the end of the 6-hour monitoring, received treatment for bradycardia, or had relevant changes on the ECG, not resolving by the end of the 6-hour monitoring (e.g. ECG at 6 hours shows a QTcF interval ≥ 500 msec), must be hospitalized overnight. For those patients, the Day 2 dose of study drug should be given in the hospital according to monitoring and discharge criteria described above.

First/redose study drug discontinuation criteria are listed below and all ECG and other reasons requiring permanent study drug discontinuation are described in [Section 5.5.9](#):

- First/Redose Criteria
 - Any hemodynamically compromising cardiac arrhythmias.
 - Patients who meet the criteria requiring overnight hospitalization again on Day 2
 - Absolute QTcF ≥ 500 msec, confirmed by repeat ECG measurements (within 24 hours).
 - New complete heart block (third degree AV block) or second degree AV block Mobitz type II.

Patient with symptomatic events or relevant changes on ECG should be followed until symptoms/ECG finding have resolved or condition has stabilized.

In addition to the above described first dose monitoring and discharge criteria required per protocol, additional monitoring post first dose may be required in some countries/regions per the local product information for Gilenya for the treatment of adult RRMS. Of note, in some regions, like in the EU, the Product Information recommends to perform additional continuous (real time) ECG monitoring during the first 6 hours post first dose.

Recommendations for the management of bradycardia

In case of bradycardia causing cardiorespiratory compromise (e.g., hypotension or peripheral hypoperfusion), atropine is recommended as the first line treatment of bradycardia. The initial dose should be 0.01 mg/kg (10 mcg/kg), up to a maximum dose of 1 mg. Furthermore, the common guidelines for treatment of bradycardia (e.g., 2005 AHA for cardiopulmonary resuscitation: pediatric advance support) should be followed as appropriate.

15 Appendix 3: Guidance on safety monitoring

15.1 Guidance on the monitoring of patients with elevated blood pressure

In children and adolescents, the normal range of blood pressure (BP) is determined by body size and age. Standardized BP norms, based on sex, age and height, as well as recommendations for diagnosing, management and treatment of high blood pressure in children and adolescents have been published ([NIH Publication No. 05-5267](#), [Lurbe et al. 2009](#)).

Using the standardized reference tables as described in these reference, if the BP is greater than the 95th percentile, BP should be staged.

- If BP is Stage 1 (95th percentile to 99th percentile plus 5 mmHg), BP measurements should be repeated within 1 month
- If BP is Stage 2 (>99th percentile plus 5 mmHg), prompt referral should be made for evaluation and treatment.
- If the patient is symptomatic, immediate referral and treatment are indicated.

The study drug should not be discontinued, unless the physician has a reason to do so. A newly diagnosed hypertension as well as an aggravation of a preexisting condition must be reported as an AE.

15.2 Guidance on monitoring of patients with elevated liver function tests

ALT/AST

In case of detection of (asymptomatic) elevated ALT/AST values >3 times the upper limit of the normal range (ULN), additional blood chemistry panel including ALT, AST, AP, GGT, total and conjugated bilirubin should be performed within a week. If the elevation is confirmed, close observation of the patient and monitoring of liver function tests (LFTs) regularly at time intervals of 1 to 4 weeks (at investigator's discretion) should be initiated.

In case of detection of elevated ALT/AST values >3 times ULN which are accompanied by symptoms (general malaise, fatigue, abdominal pain, nausea or vomiting, rash with eosinophilia) study drug needs to be discontinued immediately; hospitalize patient if clinically appropriate; establish causality. Further follow-up should include ALT, AST, TBL, Alb, PT/INR, AP and GGT until resolution^o (see below definition; frequency at investigator discretion).

In case of detection of elevated ALT/AST values ≥ 5 times the ULN, Blood chemistry liver panel including ALT, AST, AP, GGT, Alb, PT/INR, total and conjugated bilirubin must be performed within 48 hours. If ALT/AST elevation persists for more than 2 weeks, study drug administration must be interrupted. The patient should be followed up bi-weekly, until no further increase in AST/ALT is observed. Further follow-up should include ALT, AST, TBL, Alb, PT/INR, AP and GGT until resolution^o (frequency at investigator discretion).

If ALT/AST values reach 8 times the ULN, and the value is confirmed on a repeat lab within 48 hours, the study drug must be permanently discontinued ([Section 5.5.9](#)). Follow-up should include ALT, AST, TBL, Alb, PT/INR, AP and GGT until resolution^c (frequency at investigator discretion).

Alkaline phosphatase (AP)

Isolated elevation of alkaline phosphatase will not necessarily require study drug discontinuation, and would be based on the PI's discretion if the elevations were thought to be more serious in nature.

Bilirubin

In case of isolated elevation of bilirubin over 1.5 ULN (in the absence of Gilbert's syndrome), the lab needs to be repeated within 48 hours. If elevation persists, the patient must discontinue the study drug; hospitalize if clinically indicated; establish causality. Additional evaluations may be performed at the discretion of the investigator.

In case of isolated elevation of bilirubin above 2 ULN (in the absence of Gilbert's syndrome) the patient must discontinue the study drug (hospitalize if clinically indicated) and establish causality.

Follow-up on ALT, AST, TBL, Alb, PT/INR, AP and GGT until resolution^c (frequency at investigator discretion) and also test for hemolysis (e.g., reticulocytes, haptoglobin, unconjugated [indirect] bilirubin).

Concomitant elevation of ALT/AST and bilirubin (Potential Hy's Law case)

In case of elevation of ALT/AST >3 times the ULN and total bilirubin >2 times the ULN but without increase in AP >2 times the ULN (i.e. "Hy's law" criterion is met), study drug must be discontinued immediately and patient be hospitalized if clinically indicated; causality should be determined and the event reported as an AE/SAE as appropriate. The follow-up should include ALT, AST, TBL, Alb, PT/INR, AP and GGT until resolution^c (frequency at investigator discretion).

Patients with clinical symptoms; jaundice; reinitiation of study drug

Patients who develop symptoms suggestive of hepatic dysfunction, such as, but not limited to, unexplained vomiting, abdominal pain, fatigue, anorexia, dark urine, should have liver enzymes checked, and study drug should be discontinued if significant liver injury is confirmed.

In case of jaundice the patient must discontinue the study drug immediately, should be hospitalized and causality established. The follow-up should include ALT, AST, TBL, Alb, PT/INR, AP and GGT until resolution^c (frequency at investigator discretion).

Re-initiation of study drug will be dependent on whether or not another cause of liver injury is determined, and on the benefits to the patient of resuming therapy versus the risks of recurrence of liver dysfunction and per the discretion of the investigator.

Re-initiation of the study drug should only be considered once the ALT/AST decrease is below 2 times the ULN. In case of re-starting the study drug, it is recommended that ALT/AST is assessed weekly for the 1st month and then monthly for the 2nd and 3rd months. The occurrence of new elevations greater than 5 times the ULN for the ALT/AST values will lead to permanent discontinuation of the study drug ([Section 5.5.9](#)). In cases of confirmed diagnosis of hepatic dysfunction, patients should be followed until symptom resolution (see below for definition)^c or until the condition stabilizes.

Liver-specific events must be recorded in the appropriate eCRF. SAEs must be filed as appropriate.

Any interruption or discontinuation of the study drug should be clearly documented in the Dosage Administration Record eCRF. AE/SAEs must be filed as appropriate.

^c Resolution is defined as an outcome of one of the following: (1) return to baseline values, (2) stable values at three subsequent monitoring visits at least 2 weeks apart, (3) remain at elevated level after a maximum of 6 months, (4) liver transplantation, and (5) death.

15.3 Guidance on monitoring patients with symptoms of neurological deterioration, inconsistent with MS

Should a patient develop any unexpected neurological or psychiatric symptoms/signs or accelerated neurological deterioration, the investigator should schedule a complete physical and neurological examination and an MRI as soon as possible. Discontinuation of study drug should be considered. In case of new unexpected findings in the MR images, mainly if not compatible with MS lesions, it is recommended to obtain a CSF sample for cellular, biochemical and microbiological analysis (e.g. herpes virus, JC virus). Further diagnostic evaluations should be performed at discretion of the investigator. Steroid treatment should only be started once an infectious origin has been excluded or properly treated.

The MRI must be evaluated by the local neuroradiologist. A copy of the unscheduled MRI should be sent to the central MRI reading center as soon as possible. AE/SAEs need to be filed as appropriate. The investigator will contact the Medical Advisor at Novartis to discuss findings and diagnostic possibilities as soon as possible.

Only when the differential diagnosis evaluations have excluded other possible diagnosis than MS the study drug may the restart of study drug be considered.

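### Section 15.2 requires stopping study drug for raised bilirubin alone, but states no mandatory stop for some patients with the same bilirubin plus ALT/AST above 3 and below 5 x ULN

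*Protocol*

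**What the plan says.** All of these rules are in protocol Section 15.2 unless another section is named.

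- **Bilirubin, lower threshold.** "In case of isolated elevation of bilirubin over 1.5 ULN", without Gilbert's syndrome, leads to a repeat within 48 hours and, if it persists, mandatory discontinuation.
- **Bilirubin, upper threshold.** "In case of isolated elevation of bilirubin above 2 ULN", again without Gilbert's syndrome, leads to mandatory discontinuation with no repeat needed.
- **Combined rise**, under its own heading on concomitant elevation. Immediate discontinuation applies if ALT/AST is above 3 x ULN with "total bilirubin >2 times the ULN but without increase in AP >2 times the ULN". This Hy's law case is also in the list of permanent discontinuations in Section 5.5.9.
- **ALT/AST above 3 x ULN without symptoms.** A further panel is due within a week. If the rise is confirmed, liver tests follow "regularly at time intervals of 1 to 4 weeks", at the investigator's discretion. No stop is stated.
- **ALT/AST at or above 5 x ULN.** A liver panel is mandatory within 48 hours. "If ALT/AST elevation persists for more than 2 weeks, study drug administration must be interrupted".
- **ALT/AST at 8 x ULN, confirmed.** Permanent discontinuation.
- **Clinical triggers.** Symptoms with ALT/AST above 3 x ULN stop the drug at once. So does jaundice: "In case of jaundice the patient must discontinue the study drug immediately".
- **AP.** "Isolated elevation of alkaline phosphatase will not necessarily require study drug discontinuation".
- **Restart.** "Re-initiation of the study drug should only be considered once the ALT/AST decrease is below 2 times the ULN". No bilirubin level is given.

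**The concern.** Raised bilirubin together with raised transaminases is a worse panel than raised bilirubin alone. The rules should therefore be at least as strict for the combination. Here, adding an ALT/AST rise takes the patient out of the isolated-bilirubin rules, and the combined rule takes back only some of those patients. For the rest, the mandate is lost or delayed.

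The AP condition matters in this age group. The Amendment 4 rationale notes that high AP in adolescents may come from growing bone. Exclusion criterion 15 says that AP alone should not exclude a patient, so a patient can enter with AP already above 2 x ULN. While AP stays there, the combined rule cannot fire, whatever the source of the AP.

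At stake is a safety stopping rule for patients aged 10 to 17 at randomization. It applies in both blinded arms of the Core Phase and in a 60-month Extension where everyone takes fingolimod. Amendment 2 says that the liver rules were made partly more conservative because the population is new. A rule that relaxes as ALT rises does not fit that aim.

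**Working it through.** **Step 1: which rule applies to which pattern.** The inputs are the thresholds in Section 15.2, for a patient without Gilbert's syndrome, symptoms or jaundice, and below 8 x ULN. Two ALT/AST bands, two bilirubin bands and two AP bands give 2 x 2 x 2 = 8 patterns. Values are multiples of ULN; bilirubin of 1.5 to 2 means above 1.5, up to 2, and persisting on repeat.

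| ALT/AST | Bilirubin | AP | Mandatory stop or interruption now | With 'isolated' deleted |
|---|---|---|---|---|
| >3 to <5 | 1.5 to 2 | ≤2 | none | stop on 48-hour repeat |
| >3 to <5 | 1.5 to 2 | >2 | none | stop on 48-hour repeat |
| >3 to <5 | >2 | ≤2 | at once (Hy's law) | unchanged |
| >3 to <5 | >2 | >2 | none | stop at once |
| ≥5 to <8 | 1.5 to 2 | ≤2 | interrupt if >2 weeks | stop on 48-hour repeat |
| ≥5 to <8 | 1.5 to 2 | >2 | interrupt if >2 weeks | stop on 48-hour repeat |
| ≥5 to <8 | >2 | ≤2 | at once (Hy's law) | unchanged |
| ≥5 to <8 | >2 | >2 | interrupt if >2 weeks | stop at once |

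Now: 2 immediate stops, 3 interruptions only after more than 2 weeks, and 3 with no mandatory stop (2 + 3 + 3 = 8). With the word deleted: 2 Hy's law stops, 2 further stops at once and 4 on the 48-hour repeat (2 + 2 + 4 = 8). With normal ALT/AST and AP, both bilirubin bands already require discontinuation.

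**Step 2: does the result depend on what 'isolated' means?** The protocol does not define it. The rules were evaluated with ALT/AST at 3.5 and 4.9, bilirubin at 1.6, 2.0 and 2.5, and AP at 1, 1.5 and 2.5 x ULN, under four readings:

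- no other test above ULN;
- ALT/AST ≤3 and AP ≤2 x ULN;
- ALT/AST ≤3 x ULN;
- the word ignored.

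Under the first three, both profiles have no mandatory stop: bilirubin 2.5 with AP 2.5, and bilirubin 1.6 or 2.0 with any AP. Only the fourth closes the gap. Under the strictest reading the gap is wider, since a mild ALT/AST or AP rise already takes a patient out of the bilirubin rules.

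**Step 3: timing.** Bilirubin alone stops the drug on day 0 (above 2 x ULN) or by day 2 (persisting above 1.5 x ULN).

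- ALT/AST ≥5 to <8 x ULN, outside Hy's law: the panel is due by day 2, but mandatory interruption comes only after day 14. The delay is at least 14 − 0 = 14 days, or 14 − 2 = 12 days.
- ALT/AST >3 to <5 x ULN: no day is mandated. If the second panel is drawn on day 7 (an assumption; the text allows up to a week), the third falls between day 7 + 7 = 14 and day 7 + 28 = 35.

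**Step 4: other mandatory stops.** The hepatic entries in Section 5.5.9 are confirmed ALT/AST above 8 x ULN, Hy's law, and a new rise above 5 x ULN after restart. None covers the two profiles.

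**The case against.** **The gap is narrow and has backstops.** The patients concerned have combined elevations but none of the listed symptoms and no jaundice. Section 5.5.9 requires a stop if the investigator judges the risk significant and names abnormal laboratory values as a possible ground. Section 5.5.5 allows interruption on similar grounds. Section 1.1 reports no liver failure in over 4000 trial patients. This stands, and it limits the expected harm. But both routes depend on judgement, and numeric thresholds exist so that stopping does not rest on judgement alone.

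**'Isolated' might mean anything short of Hy's law.** That reading closes the gap, but it is unlikely. Section 15.2 has a separate heading for concomitant elevation, uses the same word for AP on its own, and attaches a haemolysis work-up to the isolated-bilirubin rules.

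**The split may have been deliberate.** Amendment 2 says that the liver rules follow a sponsor guideline and the advice of its liver expert team. Neither is available here, so this cannot be checked. Sites work from the protocol text, which gives no reason for the weaker instruction.

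**The remedy may cost more than it seems.** The Glossary of terms defines study drug discontinuation as permanent. The bilirubin rules use that term, whereas the rule at 5 x ULN speaks of interruption. Section 15.2 nevertheless provides for restart, so it is unsettled whether the added stops could be reversed. The only numeric restart threshold concerns ALT/AST, so a patient could meet it with bilirubin still raised. Both points stand, and the fix has to deal with them.

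**Conclusion.** The concern holds on the text and is worth correcting at the next amendment. Without Gilbert's syndrome, symptoms or jaundice, two patterns at ALT/AST above 3 and below 5 x ULN have no mandatory stop in Section 15.2: bilirubin and AP both above 2 x ULN, and bilirubin above 1.5 to 2 x ULN persisting on repeat. The same bilirubin in isolation mandates discontinuation. This assumes only that 'isolated' keeps some meaning.

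A reader might infer more than the documents support:

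- *That nothing mandatory happens at 5 x ULN or above until day 14.* The panel is mandatory within 48 hours; only interruption waits.
- *That these patients cannot be taken off drug.* They can, by investigator judgement.
- *That 3 of 8 patterns measures how often this happens.* The count describes rule coverage in a grid of equally weighted cells. Section 1.1 reports 3-fold liver enzyme rises in approximately 9-10% of patients on 0.5 mg, but the documents give no rate for the combination with bilirubin.

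The rule covers about 190 Core patients and about 162 expected to be eligible for the Extension (190 x 0.85 = 161.5). These are all patients under the rule, not the number likely to show the patterns. Amendment 7 foresaw Core end-of-study visits by June 2017 if information sufficed, so a change may mainly reach the Extension.

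**What to change.** 1. Delete 'isolated' from the two bilirubin rules in Section 15.2. Absent Gilbert's syndrome, bilirubin above 1.5 x ULN persisting on a 48-hour repeat, or any bilirubin above 2 x ULN, then requires stopping study drug whatever the ALT/AST and AP.
2. Keep the AP condition for classifying Hy's law, and leave the permanent list in Section 5.5.9 unchanged.
3. State in Section 15.2 whether these bilirubin stops are restartable, given the glossary definition. If they are, add a bilirubin condition, for example back to 1.5 x ULN or below, beside the existing ALT/AST threshold of below 2 x ULN.

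**Cost.** One word in two sentences, a short addition on restart, and a letter to sites. No new tests are needed, since bilirubin, ALT, AST and AP are already in the panel. The downside is a small, unquantified number of extra discontinuations in either arm and in the Extension. If permanent in the Core Phase, such a stop for a laboratory abnormality excludes the patient from the Extension (Section 4.2), as already happens for isolated bilirubin elevation. If restart is allowed, a patient treated for 4 weeks or more and off drug for more than 14 consecutive days needs the 6-hour first-dose monitoring again (Section 5.5.5). The primary analysis counts relapses on or off drug (Section 9.4.3), so patients who stay in the study still contribute.

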5.5.9 Discontinuation of study treatment and premature patient withdrawal

Patients may voluntarily withdraw from the study for any reason at any time. They may be considered withdrawn if they state an intention to withdraw, fail to return for visits, or become lost to follow-up for any other reason.

If premature withdrawal occurs for any reason, the investigator must make every effort to determine the primary reason for a patient's premature withdrawal from the study and record this information on the Study Phase Completion eCRF for Core Phase and Study Completion eCRF for Extension Phase.

Study drug must be discontinued for a given patient if the investigator determines that continuing it would result in a significant risk for that patient. The following conditions/events may be considered sufficient to support a decision about the study drug discontinuation in individual cases:

- Serious adverse event (e.g. diagnosed malignancy)
- Abnormal laboratory value(s) or abnormal test result(s); see below and [Appendix 3](#) for guidance for safety monitoring
- Sexual activity in girls who do not agree to the use of contraception as defined in [Section 6.6](#)
- Use of prohibited medications ([Section 5.5.8](#))
- Adverse events
- Protocol deviation
- Unsatisfactory therapeutic effect
- Patient's condition no longer requires study treatment
- Administrative problems (e.g. patient's non-compliance)

The following conditions must result in permanent study drug discontinuation:

- Hepatic ([Appendix 3: Section 15.2](#))
 - Increase in ALT or AST >8 x ULN (with confirmed value on a repeat lab within 48 hours) or
 - “Hy’s law” criterion is met or
 - The occurrence of new elevations greater than 5 X the ULN for ALT/AST in patients where study drug was re-initiated after drug stoppage for liver enzyme elevations.
- Ophthalmic ([Appendix 3: Section 15.8](#))
 - Diagnosis of macular edema.
 - If systemic immunosuppressive treatment (other than corticosteroids) is required for treatment of uveitis.
- First/Redose Criteria ([Appendix 2](#))
 - Any hemodynamically compromising cardiac arrhythmias.
 - Patients who meet the criteria requiring overnight hospitalization again on Day 2.
- ECG abnormalities (all visits including first/redose)
 - Absolute QTcF \geq 500 msec, confirmed by repeat ECG measurements (within 24 hours).
 - New complete heart block (third degree AV block) or second degree AV block Mobitz type II.
- ECG abnormalities (non-first/redose visits)

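### Protocol 5.5.9 makes Hy's law a permanent stop, but the re-initiation paragraph in 15.2 does not exclude it, so a site working from 15.2 alone could restart study drug

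*Protocol*

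**What the plan says.** Section 5.5.9 separates discretionary grounds for stopping from a mandatory list headed "The following conditions must result in permanent study drug discontinuation". The mandatory list has three hepatic items:

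- "Increase in ALT or AST >8 x ULN (with confirmed value on a repeat lab within 48 hours) or";
- the Hy's law criterion, with no qualification as to cause;
- "The occurrence of new elevations greater than 5 X the ULN for ALT/AST in patients where study drug was re-initiated after drug stoppage", where the stoppage was for liver enzyme elevations.

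The hepatic bullet itself refers the reader to Section 15.2.

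Section 15.2 (Appendix 3) defines Hy's law as ALT/AST above 3 x ULN with total bilirubin above 2 x ULN and alkaline phosphatase not above 2 x ULN. It requires drug to be stopped at once and causality to be determined. Under the next sub-heading it states: "Re-initiation of study drug will be dependent on whether or not another cause of liver injury is determined". Restart also depends on benefit against risk and the investigator's discretion, and may be considered only once ALT/AST is below 2 x ULN.

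Three other places bear on the point. Section 6.5.4 names 5.5.9 as the place where the permanent blood chemistry criteria are listed. Appendix 2, in its first-dose guidance, says that "all ECG and other reasons requiring permanent study drug discontinuation are described in" Section 5.5.9. Section 5.5.5 describes re-initiation after an interruption as decided by the investigator in agreement with the sponsor, case by case.

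**The concern.** The Hy's law paragraph of 15.2 asks the site to establish the cause. The paragraph that follows makes the cause a test for restarting. A site that stops drug for Hy's law, finds another explanation and sees ALT/AST fall below 2 x ULN would, on 15.2 alone, appear to have met the conditions for considering a restart. Section 5.5.9 makes the same event a permanent stop whatever the cause.

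At stake is how consistently a serious hepatic stop is handled in a paediatric trial. How the stop is classified also has consequences within the study:

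- **Schedule.** Under Section 6, premature discontinuation brings end-of-treatment assessments, a 3-month follow-up visit and then the abbreviated schedule.
- **Extension entry.** Under Section 4, patients who complete the Core Phase on drug enter the Extension Phase without further criteria. Those who discontinued early for an adverse event, laboratory abnormality or other safety reason meet an exclusion criterion.
- **Tables and supportive analyses.** The disposition tables (SAP 3.2), the on-drug relapse analysis (SAP 4.2.1.1) and the per-protocol set (SAP 3.1) all reflect when a patient stopped for good.

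**Working it through.** No sample size, power or event figure is involved, so the check is a side-by-side reading of the hepatic rules.

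| Event | Section 5.5.9 | Section 15.2 |
|---|---|---|
| ALT/AST at 8 x ULN, confirmed | Permanent, if above 8 x ULN | Permanent, with reference to 5.5.9, if values reach 8 x ULN |
| New ALT/AST above 5 x ULN after restart | Permanent | Permanent, with reference to 5.5.9 |
| Hy's law | Permanent | Stop immediately; neither marked permanent nor referred to 5.5.9 |
| Jaundice | Not on the mandatory list | Mandatory stop, permanence not stated |
| Isolated bilirubin above 1.5 x ULN and persisting, or above 2 x ULN | Not on the mandatory list | Mandatory stop, permanence not stated |
| ALT/AST above 3 x ULN with symptoms | Not on the mandatory list | Mandatory stop, permanence not stated |
| ALT/AST at or above 5 x ULN for more than 2 weeks | Not on the mandatory list | Drug interrupted |

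1. Of the three hepatic items in 5.5.9, 15.2 marks two as permanent and cross-refers them. Hy's law is the only one left unmarked.

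2. The restart paragraph excepts no event. For confirmed 8 x ULN this does little harm, because that paragraph of 15.2 already says the stop is permanent. For Hy's law nothing inside 15.2 does the same work.

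3. The verb does not settle it. The glossary defines study drug discontinuation as permanent, and 15.2 uses a different word, *interrupted*, for a temporary stop. But Section 15.4 (lymphopenia) requires drug to be discontinued and then allows re-initiation once counts recover. A reader of Appendix 3 therefore cannot infer permanence from *discontinued* alone.

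4. Section 5.5.9 names Hy's law without defining it, so a site must go to 15.2 to recognise the event. It then meets the unmarked stop and, shortly after, the general restart rule.

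5. The sections also differ on who decides. Section 15.2 leaves restart to the investigator's discretion, while 5.5.5 brings in the sponsor.

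6. On the 8 x ULN limit, "If ALT/AST values reach 8 times the ULN, and the value is confirmed on a repeat lab within 48 hours" includes exactly 8 x ULN and the 5.5.9 wording does not. The two rules differ only at equality.

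**The case against.** The strongest reply is that Hy's law does have one stated answer. Section 5.5.9 lists it as permanent and points to 15.2, and 6.5.4 names 5.5.9 as the place for permanent blood chemistry stops. Read together, the word *immediately* in 15.2 gives timing and says nothing about duration. General restart text should not override a named permanent stop. Section 5.5.5 also puts sponsor agreement in front of a restart. All of this stands, and it limits the finding: a restart is something 15.2 fails to exclude, not something it grants. It does not remove the gap, because 15.2 marks the other two permanent stops and omits this one.

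Three stronger readings are tempting and are not supported.

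- **The stops found only in 15.2 contradict 5.5.9.** One of them reads "In case of jaundice the patient must discontinue the study drug immediately, should be hospitalized and causality established", and it is missing from the mandatory list. But that list covers permanent stops only, and its third item itself foresees restart after some liver stops. The discretionary list covers abnormal laboratory values and points to Appendix 3. The restart text sits under a heading that names jaundice. These stops can be read without conflict as restartable; their status is merely unstated.
- **A patient stopped for isolated bilirubin could restart the same day because ALT/AST is already below 2 x ULN.** That threshold is necessary, not sufficient. Section 15.2 also requires causality to be established and makes restart depend on cause and benefit-risk.
- **The adult enzyme-elevation rate in Section 1.1 shows how often this matters.** It describes past adult experience of 3-fold ALT and GGT rises and says nothing about how often Hy's law or the other stops occur. Asymptomatic ALT/AST above 3 x ULN leads to monitoring under 15.2.

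**Conclusion.** The point holds for Hy's law. Section 5.5.9 makes it a mandatory permanent stop, and the re-initiation paragraph in 15.2 does not exclude it, so the same event can lead to different handling depending on which section a site uses. A reader might go further and infer that the protocol contradicts itself across all its hepatic stops, or that Hy's law has no settled status. The texts do not support either inference.

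No numerical size can be given, because the documents contain no frequency for Hy's law events. The importance comes from the seriousness of the event. The primary analysis is not affected: Protocol 9.4.3 and SAP 4.2.1.2 count relapses whether the patient is on or off drug. The on-drug analysis runs to the recorded last core dose date, so its definition does not depend on how 15.2 is read, although a restart would move that date for the patient concerned.

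The conclusion assumes that some sites use Appendix 3 as working guidance without returning to 5.5.9. The 8 x ULN inequality and the unstated status of the stops found only in 15.2 are secondary clarifications.

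**What to change.** Reconcile 5.5.9, 15.2 and 5.5.5 so that the scope of the re-initiation paragraph agrees with the permanent-stop list for Hy's law. In practice:

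- name in that paragraph the hepatic stops it covers;
- give Hy's law the same status in both sections, with the cross-reference that 15.2 already uses for the other two items;
- say in 15.2 whether the sponsor agreement described in 5.5.5 applies.

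In the same edit, use one inequality for the 8 x ULN limit. State for jaundice, isolated bilirubin and symptomatic ALT/AST above 3 x ULN whether the stop is permanent or restartable. Which clinical rule applies in each case is for the sponsor to decide; the review asks only that the passages agree.

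The cost is a few sentences of protocol text, made through a written amendment as Section 11.1 requires. It adds no visit, test or data collection.
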